## 7.6. Blinding

The study is open label, neither the subject, HCP, site staff, or sponsor is blinded to treatment assignment.

## 7.7. Preparation/Handling/Storage/Accountability

1. The investigator or designee must confirm appropriate temperature conditions have been maintained during transit for all study treatment received and any discrepancies are reported and resolved before use of the study treatment.
2. Only subjects enrolled in the study may receive study treatment and only authorised site staff may supply or administer study treatment. All study treatments must be stored in a secure, environmentally controlled, and monitored (manual or automated) area in accordance with the labeled storage conditions with access limited to the investigator and authorised site staff.

3. The investigator, institution, or the head of the medical institution (where applicable) is responsible for study treatment accountability, reconciliation, and record maintenance (i.e. receipt, reconciliation, and final disposition records).
4. Further guidance and information for the final disposition of unused study treatment are provided in the SRM.

Under normal conditions of handling and administration, study treatment is not expected to pose significant safety risks to site staff.

A Material Safety Data Sheet (MSDS)/equivalent document describing occupational hazards and recommended handling precautions either will be provided to the investigator, where this is required by local laws, or is available upon request from GSK.

## **7.8. Treatment Compliance**

The primary measure of treatment compliance for both Relvar/Breo ELLIPTA and Salbutamol MDI will be captured by the respective sensor for those treatments. However, the date of prescription and date of return of the inhaler, as well as start and finished dose count on each Relvar/Breo ELLIPTA, will be recorded in source documents at the dispensing visit and also transferred to the eCRF.

## **7.9. Concomitant Therapy**

All medications for asthma, excluding biological therapy and for other disorders that are not contra indicated in asthma, or prohibited in this study, may be continued throughout the study.

Please consult the prescribing information for the full list of medications which need to be used with caution:

Beta-blockers: Use with caution. May block bronchodilatory effects of beta-agonists and produce severe bronchospasm.

Diuretics: Use with caution. Electrocardiographic changes and/or hypokalemia associated with non-potassium-sparing diuretics may worsen with concomitant beta-agonists.

Non-study asthma medications: A detailed history of previous 3 months and up to 12 months prior to inclusion, as available, for prescriptions for maintenance medications (ICS/LABA combination) will be captured in the subjects eCRF and also any other ongoing asthma medications at inclusion.

Any medication or vaccine of relevance to the study or prescribed for safety events, including exacerbations experienced during the study, that the subject is receiving at the time of enrolment or receives during the study must be recorded in the eCRF in addition to medical records. As minimum the following will be needed:

- reason for use
- dates of administration including start and end dates

- dosage information including dose and frequency

Over-the-counter medicines, vitamins, and/or herbal supplements are not required to be captured.

The Medical Monitor should be contacted if there are any questions regarding concomitant or prior therapy.

## **7.10. Prohibited Concomitant Medication**

Subjects must abstain from taking the following medications from 5 days prior to the first dose of study medication until completion of the follow-up visit.

- Strong cytochrome P450 3A4 inhibitors (e.g., ketoconazole)
- Monoamine oxidase inhibitors and tricyclic antidepressants:
- Subjects must never have been treated with a biological therapy for asthma e.g. omalizumab, mepolizumab.

**Patients using Relvar/Breo ELLIPTA should not use another medicine containing a LABA (e.g., salmeterol, formoterol fumarate, arformoterol tartrate, indacaterol) for any reason.**

Do not use in combination with an additional medicine containing a LABA because of risk of overdose.

For full list of cautions for use and medicine interactions please consult the prescribing information and/or consult the study Medical Monitor if in doubt.

## **7.11. Treatment after the End of the Study**

There is no plan to continue to provide treatment following the end of the study. The investigator is responsible for ensuring that consideration has been given to the post-study care of the subject's medical condition, whether or not GSK is providing specific post-study treatment.

Medications initiated after completion of the assessments at V10 or the EW visit will not be recorded in the eCRF unless taken to treat an AE or asthma exacerbation. subjects who have completed the EW visit are allowed to use any medications prescribed by the Investigator or primary care physician.

## **8. DISCONTINUATION CRITERIA**

Subjects that permanently stop study treatment (any aspect of the CIS) are encouraged to remain in the study. Subjects have the right to discontinue study treatment before the end of the study. A subject may also be asked to discontinue study treatment at the investigator's discretion.

Subjects who withdraw from study treatment prematurely (for any reason) should, where possible, continue to be followed-up as per protocol until the completion of the Safety Follow-up assessments. If patients want to discontinue use of the CIS but will continue taking the Relvar/Breo ELLIPTA DPI then they will be given the option to continue to remain in study if they continue using the clip-on sensor for ELLIPTA. If this is not possible, the Investigator must encourage the subject to participate in as much of the study as they are willing (or able) to. For those subjects who do not want to use the sensor during the study, their health outcome information will be collected along with any additional adherence data. Likewise, subjects who change their dose of Relvar/Breo (FF/VI) at the discretion of the investigator during the study will be given the option to remain on the study, all information will continue to be collected for the duration of the study. However, subjects who permanently discontinue from Relvar/Breo ELLIPTA should be withdrawn from the study.

A subject may be withdrawn from study treatment at any time. A reason for premature discontinuation of study treatment must be captured in the eCRF.

## **8.1. Discontinuation of Study Treatment**

[figure not shown]
### **8.1.1. Liver Chemistry Stopping Criteria**

There are no scheduled blood tests in this study. If however, the subject has a routine blood test during the study and the results suggest abnormal liver function, then the liver stopping criteria will apply.

**Liver chemistry stopping and increased monitoring criteria** have been designed to assure subject safety and evaluate liver event etiology (in alignment with the FDA premarketing clinical liver safety guidance). These protocol guidelines are in alignment with FDA premarketing clinical liver safety guidance:

<http://www.fda.gov/downloads/Drugs/GuidanceComplianceRegulatoryInformation/Guidances/UCM174090.pdf>.

Discontinuation of study treatment for abnormal liver tests should be considered by the investigator when a subject meets one of the conditions outlined in the algorithm, see [Appendix 5](#), or if the investigator believes that it is in the best interest of the subject.

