
 
• Immediately discontinue study treatment
 
• Report the event to GSK within 24 hours
 
• Complete the liver event CRF and complete an SAE data collection tool if the event also meets the criteria for an SAE
 
• Perform liver event follow up assessments
 
• Monitor the subject until liver chemistries resolve, stabilize, or return to within baseline (see MONITORING below)
 
• Do not restart/rechallenge subject with study treatment
 
• Permanently discontinue study treatment and continue subject in the study for any protocol specified follow up assessments
 
 
MONITORING:
 
For bilirubin or INR criteria:
 
 
• Repeat liver chemistries (include ALT, AST, alkaline phosphatase, bilirubin) and perform liver event follow up assessments within 24 hrs
 
	
 
• Viral hepatitis serology
 
• Obtain INR and recheck with each liver chemistry assessment until the transaminases values show downward trend
 
• Only in those with underlying chronic Hepatitis B at study entry (identified by positive Hepatitis B surface antigen) quantitative Hepatitis B DNA and Hepatitis delta antibody.
 
• Serum creatine phosphokinase (CPK) and lactate dehydrogenase (LDH).
 
• Fractionate bilirubin, if total bilirubin <math>\geq</math> 2xULN
 
• Obtain complete blood count with differential to assess eosinophilia
 
• Record the appearance or worsening of clinical symptoms of liver injury, or hypersensitivity, on the AE report form
 
• Record use of concomitant medications on the concomitant medications report form including acetaminophen, herbal
 

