
 
Monitor subjects twice weekly until liver chemistries resolve, stabilize or return to within baseline
 
A specialist or hepatology consultation is recommended
 
 
For All other criteria:
 
 
Repeat liver chemistries (include ALT, AST, alkaline phosphatase, bilirubin) and perform liver event follow up assessments within 24-72 hrs
 
Monitor subjects weekly until liver chemistries resolve, stabilize or return to within baseline
 
	
remedies, other over the counter medications.
 
 
Record alcohol use on the liver event alcohol intake case report form (CRF) page
 
 
For bilirubin or INR criteria:
 
 
Anti-nuclear antibody, anti-smooth muscle antibody, Type 1 anti-liver kidney microsomal antibodies, and quantitative total immunoglobulin G (IgG) or gamma globulins.
 
Serum acetaminophen adduct high performance liquid chromatography (HPLC) assay (quantifies potential acetaminophen contribution to liver injury in subjects with definite or likely acetaminophen use in the preceding week [James, 2009]).
 
Liver imaging (ultrasound, magnetic resonance, or computerised tomography) and /or liver biopsy to evaluate liver disease: complete Liver Imaging and/or Liver Biopsy CRF forms.
 

---	---

1. Serum bilirubin fractionation should be performed if testing is available. If serum bilirubin fractionation is not immediately available, discontinue study treatment for that subject if alanine aminotransferase (ALT)  $\geq 3\times\text{ULN}$  and bilirubin  $\geq 2\times\text{ULN}$ . Additionally, if serum bilirubin fractionation testing is unavailable, **record presence of detectable urinary bilirubin on dipstick**, indicating direct bilirubin elevations and suggesting liver injury.
2. All events of ALT  $\geq 3\times\text{ULN}$  and bilirubin  $\geq 2\times\text{ULN}$  ( $>35\%$  direct bilirubin) or ALT  $\geq 3\times\text{ULN}$  and INR  $>1.5$ , if INR measured which may indicate severe liver injury (possible 'Hy's Law'), **must be reported as an SAE (excluding studies of hepatic impairment or cirrhosis)**; INR measurement is not required and the threshold value stated will not apply to subjects receiving anticoagulants

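### Protocol 8.1.1 leaves a liver stop to be considered where Appendix 5 makes it mandatory, and Section 8 and Appendix 5 disagree on whether the subject then stays in the study

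*Protocol*

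**What the plan says.** **Action on a liver finding.** Protocol 8.1.1 notes that no blood tests are scheduled. If a routine test suggests abnormal liver function, "then the liver stopping criteria will apply". A later sentence in the same section reads: "Discontinuation of study treatment for abnormal liver tests should be considered by the investigator when a subject meets one of the conditions", with a reference to Appendix 5. That sentence ends with a separate limb that allows a stop on the investigator's view of the subject's best interest.

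Appendix 5 lists the stopping criteria and then the required actions. These include "Immediately discontinue study treatment", "Do not restart/rechallenge" and "Permanently discontinue study treatment and continue subject in the study for any protocol specified follow up assessments". Footnote 1 is equally direct for a subject who meets its ALT and bilirubin limits: if bilirubin fractionation "is not immediately available, discontinue study treatment for that subject".

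**Study status after a permanent stop.** Section 8 opens with "Subjects that permanently stop study treatment (any aspect of the CIS) are encouraged to remain in the study", but later in the same section says "subjects who permanently discontinue from Relvar/Breo ELLIPTA should be withdrawn from the study". Appendix 5, as quoted above, keeps the subject in the study for follow-up.

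**The concern.** A safety stopping rule should have one reading. Here one sentence asks the investigator to weigh discontinuation, while the appendix it refers to has already decided the matter. A site that relies on the body text could leave a subject on Relvar/Breo after an ALT result for which the appendix demands a permanent stop, and could cite the protocol for doing so.

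The status conflict is a second, smaller problem. A site that follows Section 8 withdraws the liver-stopped subject and completes the early-withdrawal assessments. A site that follows Appendix 5 keeps the subject in the study. At stake are consistent handling of a safety event and a clear disposition record. The efficacy result is not at issue.

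**Working it through.** The plan gives no figure to reproduce, and the only arithmetic is a count. The check is a comparison of texts.

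1. **Same trigger?** Yes. 8.1.1 takes its conditions from Appendix 5. The appendix table has six rows: ALT absolute (1 condition), ALT increase (2), bilirubin (1), INR (1), cannot monitor (2) and symptomatic (1). That makes 1 + 2 + 1 + 1 + 2 + 1 = 8 conditions. The actions block is not divided by condition; only the monitoring schedule separates bilirubin or INR criteria from the rest. All 8 of 8 conditions therefore carry the mandatory stop in the appendix and the softer instruction in 8.1.1.

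2. **Same action?** No. Appendix 5 leaves no choice about whether, when or for how long to stop. 8.1.1 makes stopping a matter for consideration. The soft verb cannot be confined to other situations, because it governs both limbs of its sentence: meeting a listed condition, and the investigator's own judgement.

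3. **Does any text rank the two?** No sentence gives one priority. The opening of 8.1.1 points towards the mandatory reading, which makes the section inconsistent within itself.

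4. **Example.** Suppose a routine test returns ALT at or above 8 times the upper limit of normal, the first Appendix 5 criterion. Under the appendix, treatment stops at once and for good. Under the later sentence of 8.1.1, continuing after consideration is allowed.

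5. **Status.**
   - Section 7 defines study treatment to include marketed products, and the table in 7.1 names Relvar/Breo ELLIPTA under that term.
   - A permanent stop under Appendix 5 is therefore a permanent Relvar/Breo discontinuation.
   - That triggers the withdrawal sentence in Section 8, which contradicts the Appendix 5 instruction to keep the subject in the study.
   - The withdrawal sentence is absent from Section 8 of the original protocol (22-JUN-2017) and present in the current one. The Appendix 5 instruction is the same in both, so it was not aligned when the sentence came in.

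6. **Practical difference.** Appendix 5 requires liver monitoring until the chemistries resolve, stabilise or return to baseline, whichever status applies. What differs is whether the subject leaves through an early-withdrawal visit or stays for the remaining scheduled visits, up to V11 at day 175.

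**The case against.** **The appendix plainly governs.** 8.1.1 says that the criteria will apply and points to Appendix 5, the only place where actions are set out. Most investigators would probably read it that way. This lowers the likely harm, but the contrary sentence is still there. 8.1.1 also mentions an algorithm, and a figure under 8.1 is not shown in the available text. Whatever it contains, it cannot remove the sentence.

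**Section 8 already asks for follow-up.** It says that subjects who stop study treatment early, for any reason, should where possible be followed through to the safety follow-up. Appendix 5 speaks of follow-up assessments specified in the protocol. The two are close in aim. This softens the conflict without removing it, because being withdrawn and being continued in the study remain different dispositions.

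**The object of the stop might seem unclear.** Section 8 glosses study treatment as any aspect of the connected system, so a reader might infer that the liver rule is not tied to the drug. Section 7 and the table in 7.1 answer this, and rechallenge after an ALT rise makes sense only for a drug. Naming Relvar/Breo is tidier, but there is no separate defect here.

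**The SAP might seem to need correcting too.** SAP 10.5.1 says that participants who permanently stop Relvar/Breo may continue in the study, which a reader might set against current Section 8. The SAP has to cover the whole trial. The original protocol encouraged subjects who stopped study treatment to stay and complete visits, and recruitment was under way before Amendment 01 (10-SEP-2018). SAP 10.5.1, and pattern D in 10.5.3.1 (sensor and ELLIPTA stopped together without leaving the study), must therefore accommodate anyone who stopped and stayed under that version. Narrowing them would be wrong. This objection stands in full.

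**Conclusion.** The point holds as a wording conflict in a safety rule. For all eight Appendix 5 conditions, 8.1.1 gives a discretionary instruction where the appendix gives a mandatory one. Section 8 and Appendix 5 also assign different study status after the resulting Relvar/Breo stop. It should be fixed, but the exposure is small: blood tests are unscheduled, and the documents give no rate of liver findings.

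A reader might infer that study status changes how the subject counts in the Month 4 to 6 adherence analysis: data after the stop excluded if the subject stays, imputed as missing at random (MAR) if withdrawn. The SAP does not settle this.

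- The estimation schematic in 10.5.3.1 does make imputation after a combined sensor and ELLIPTA stop depend on concurrent withdrawal.
- Table 3 in 7.1.4 limits MAR imputation to withdrawals unrelated to ELLIPTA discontinuation. A withdrawal forced by Section 8 after a Relvar/Breo stop arguably fails that test.
- Step 5 of 10.5.3.1 gives full weight to stops for reasons unrelated to ELLIPTA, with no condition on withdrawal.

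Because these texts disagree on which rule applies, no contrast in weights can be stated, and no effect on the primary result is claimed.

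The QTc rule in 8.1.2 has a change-from-V1 criterion although no V1 ECG is planned. The absolute limits still operate without one, so that is an optional clarification only.

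**What to change.** 1. **Protocol 8.1.1.** Replace the sentence on considering discontinuation with wording such as: *When a subject meets any Appendix 5 criterion, Relvar/Breo must be discontinued as set out there. For other liver findings, discontinuation is at the investigator's discretion.*
2. **Protocol Section 8.** Add to the withdrawal sentence: *except subjects stopped under Appendix 5, who remain in the study for the follow-up specified there.*
3. **SAP.** Leave 10.5.1 and pattern D unchanged.
4. **Optional.** In 8.1.2, apply the change-from-V1 criterion only where a pre-treatment ECG is on file, and rely on the absolute limits otherwise.

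The cost is one sentence in each of two protocol sections, plus one if the QTc clarification is taken up. Appendix 2 requires ethics approval for amendments, so the changes are best carried in the next one. They add no tests, visits or derivations. They clarify the rule and would not detect more liver events.

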### 8.1.2. QTc Stopping Criteria

ECGs are not planned at Screening or during this study. However, if during the study a subject has an ECG performed the following stopping criteria apply and treatment should be withdrawn:

A subject who meets the bulleted criteria below will be withdrawn from the study:

- $QTcF > 500$  msec or uncorrected  $QT > 600$  msec
- Change from V1 baseline:  $QTcF > 60$  msec

For patients with underlying **bundle branch block**, follow the discontinuation criteria listed below:

Discontinuation QTc with Bundle Branch Block	
$< 450$ msec	$> 500$ msec
$450 - 480$ msec	$\geq 530$ msec [Note: $QTc(F) > 500$ msec for Korean subjects]

### 8.2. Withdrawal from the Study

- A subject may withdraw from the study at any time at his/her own request, or may be withdrawn at any time at the discretion of the investigator for safety, behavioural, compliance to protocol or administrative reasons.

- Subjects should be reminded at each visit that if they do choose to withdraw themselves then, they should contact the Investigator or Study staff as soon as possible and arrange an EW visit.
- Female subject will be withdrawn if they produce a positive pregnancy test whilst on the study.
- If the subject withdraws consent for disclosure of future information, the sponsor may retain and continue to use any data collected before such a withdrawal of consent.

Refer to the Section 2 for data to be collected at the time of EW from the study

### **8.3. Lost to Follow Up**

A subject will be considered lost to follow-up if he or she repeatedly fails to return for scheduled visits and is unable to be contacted by the study site.

The following actions must be taken if a subject fails to return to the clinic for a required study visit:

- The site must attempt to contact the subject and reschedule the missed visit as soon as possible and counsel the subject on the importance of maintaining the assigned visit schedule and ascertain whether or not the subject wishes to and/or should continue in the study.
- Before a subject is deemed lost to follow up, the investigator or designee must make every effort to regain contact with the subject (where possible, 3 telephone calls and, if necessary, a certified letter to the subject's last known mailing address or local equivalent methods). These contact attempts should be documented in the subject's medical record.
- Should the subject continue to be unreachable, he/she will be considered to have withdrawn from the study with a primary reason of lost to follow-up.

## **9. STUDY ASSESSMENTS AND PROCEDURES**

Study procedures and their timing are summarised in Section 2.

Protocol waivers or exemptions are not allowed

Immediate safety concerns should be discussed with the sponsor immediately upon occurrence or awareness to determine if the subject should continue or discontinue study treatment.

Adherence to the study design requirements, including those specified in the Section 2, is essential and required for study conduct.

All screening evaluations must be completed and reviewed to confirm that potential subjects meet all eligibility criteria. The investigator will maintain a screening log to record details of all subjects screened and to confirm eligibility or record reasons for screening failure, as applicable.

Procedures conducted as part of the subject's routine clinical management (e.g., blood count) and obtained before signing of the informed consent form (ICF) may be utilized for screening or baseline purposes provided the procedure met the protocol-specified criteria and was performed within the time frame defined in the Section 2.

## **9.1. Efficacy Assessments**

### **9.1.1. Primary, Secondary and Other Adherence Measures**

The Primary, Secondary and Other adherence endpoint (adherence to maintenance medication) data is collected by the Clip-on Sensor for ELLIPTA and records the time and date when the ELLIPTA cover is opened and closed.

The sensor will be attached to subjects ELLIPTA Relvar/Breo treatment from start of run-in until V10. References and material for fitting the sensors, downloading the app and other aspects of using the CIS are included in the SRM.

